### **10 Recruitment Setting**

Adult patients with hyperacute stroke presenting at emergency departments and hyperacute stroke units in England. The trial setting will be in secondary care at NIHR Clinical Research Network sites with dedicated Research coordinators who will facilitate recruitment and follow up discharge or death.

### **11 Randomisation**

Patients will be randomised 1:1 to receive either 5 mg transdermal GTN versus sham transdermal DuoDERM hydrocolloid dressing placed on the back or shoulders for two days. Randomisation will be performed by the Stroke Trials Unit (STU) in Nottingham and involve computerised stratification by stroke type (IS or not known; ICH) and minimisation on age, severity, time, systolic blood pressure and candidate for or received reperfusion therapy. Patients, relatives, researchers, and outcome assessors will be masked to treatment allocation.

### **12 Statistical interim analyses and stopping guidance.**

#### **12a Interim analyses:**

An independent Data Monitoring Committee (DMC) will be established. The DMC will receive safety reports twice yearly, or more if requested, and perform unblind reviews of safety and efficacy data. The DMC have responsibility to monitor SAEs and neurological deterioration and outcome in IS and ICH separately. No interim analysis will be performed.

**12b Adjustments of significance level:**

There is no planned adjustment.

**12c Stopping rules:**

There are no formal stopping rules since the main aim of the study is to study feasibility. The trial will not be discontinued unless the safety of the participants is likely to be compromised. The trial may be terminated by either the TSC, the sponsor or the funder if there is overwhelming evidence of major safety concerns, new information becomes available that makes the trial unsafe or irrelevant or there is issues with trial conduct (e.g., loss of resources).

**13 Timing of final analyses**

Prior to each database lock, the trial managers/trial co-ordinators will chase outstanding data queries and the lock will take place in accordance with the documented data lock procedure once notification has been given to the trial programmer by the chief investigator.

Both interim and final locks will be documented and primarily consist of the creation of a read-only copy of the live database, with each copy available to the trial statistician via the online data extract process.

**14 Table C.-Timing of outcome assessments**

Assessments	Screen	Day 0 Baseline Pre- treatment	Day 0 Post- treatment	Day 1 During treatment	Day 2 After treatment	Discharge, Death	Day 90 Telephone
Face-to-face							
Clinical assessment	X 				X	X	
Eligibility screening	X						
CT Scan		X 	or X 				
Consent		X		or X	or X		
Randomisation		X					
GTN/Sham patch			X	X			
mRS		X 					
U & E FBC		X 					
Blood pressure		X 	X	X			
NIHSS		X 			X		
DSRS		X			X		
Blood biomarkers		X 			X 		

Hospital utilisation						X 	
Listed events				X 	X 		
SAEs, non-fatal			X	X	X		
SAEs fatal				X	X	X	X 
mRS							X 
Barthel Index							X 
EuroQoL							X 
Cognition (t-MMSE, TICS)							X 
Mood (ZDS)							X 

CT: Computerised tomography

NIHSS: National Institutes of Health stroke scale

MMSE: Mini-Mental State Examination

mRS modified Rankin scale

SAEs: Serious Adverse Events

1. Routine as part of clinical practice

2. Pre-morbid mRS

3. Biomarkers: soluble markers, genetics

4. Open-label blood pressure lowering, intravenous thrombolysis, mechanical thrombectomy, hyperacute stroke unit, Stroke Rehabilitation Unit, physiotherapy, occupational therapy, speech & language therapy, surgery for IS – hemicraniectomy, surgery for ICH, days in intensive/critical care unit.

5. Hypotension, hypertension, headache, infection

6. mRS [0 to 5, death=6], NIHSS [0 to 42, death=43], DSRS [0 to 12, death=13], GCS [3 to 15, death=2], BI [0 to 100, death=-5], EQ-5D [-0.5 to 1.0, death=0], EQ-VAS [0 to 100, death=-1], t-MMSE [0 to 22, death=-1], TICS-m [0 to 39, death=-1] and ZDS [ $\geq 70$ , death=102.5].

## **SECTION 4. STATISTICAL PRINCIPLES**

### **15 Statistical significance**

#### ***15a Level of statistical significance and p values***

The results of analyses and comparisons will be shown with  $p \leq 0.05$ .

#### ***15b Confidence intervals***

The results of analyses and comparisons will be shown with 95% confidence intervals.

### **16 Adherence**

Compliance will be assessed by examining the participant's drug chart and recording evidence of treatment administration. Adherence will be recorded on the case report forms after treatment has been completed (day 2).

**16a Definition:**

Adherence will be considered sufficient if  $\geq 90\%$  of participants receive their first active/sham treatment (**see Table 6**).

**17 Protocol deviations:**

All protocol deviations and violations must be reported immediately to the Chief Investigator, via the online electronic case report form. The CI will notify the Sponsor if a deviation or violation has an impact on participant safety or integrity of the trial data. The Sponsor will advise on appropriate measures to address the occurrence, which may include reporting of a serious GCP breach, internal audit of the trial and seeking counsel of the trial committees.

**17a Protocol deviation presentation:**

Listing of violations and deviations.

**18 Analysis populations**

All available data will be used, including overall patients presenting in clinic and screening data where available. Missing data will be reported.

1. Intention-to-treat population (ITT): summaries by treatment group will be provided according to the treatment the participant was randomised to.
2. Safety population: All participants who were randomised will be summarised according to the treatment they received irrespective of treatment.

**SECTION 5. TRIAL POPULATION****19 Screening data**

Overall patients presenting in clinic and screening data where available will be kept on screening logs and will be presented.

**20 Eligibility****20a Inclusion**

1. 120 adults (age  $\geq 18$  years) with presentation compatible with stroke
2. Treatment 3-5 hours post ictus (for patients with wake-up stroke, treatment no more than 5 hours after patient awakens)
3. One or more of the following symptoms present at time of enrolment:
  - a. Dysphasia.
  - b. Neglect (NIHSS 1-2)
  - c. Hemianopia (NIHSS 1-3)
  - d. Limb weakness (NIHSS on affected arm and/or leg 1-4)
  - e. Systolic BP ( $\geq 120$  mmHg)
4. If a CT/MR scan has already been performed, then it shows acute intracerebral haemorrhage or ischaemic stroke, or is normal.
5. Waiver of consent for treatment to ensure GTN given in 3-5-hour time window (and thrombolysis not delayed if ischaemic stroke).

**20b Exclusion**

1. mRS  $\geq 4$
2. Glucose (BM stix or equivalent)  $< 3$  mmol/l
3. Glasgow coma scale  $\leq 8$
4. Witnessed seizure at presentation.
5. Known life expectancy  $< 6$  months.
6. Patient presenting with sensory symptoms only.

7. Known stroke mimic, aneurysmal subarachnoid haemorrhage, or haemorrhage due to venous thrombosis.
8. Systolic blood pressure <120 mmHg
9. Known allergy to glyceryl trinitrate (Transiderm-Nitro) patch.
10. Known sensitivity to Duoderm hydrocolloid dressing.
11. Planned for palliative care only.
12. Recent use of phosphodiesterase type 5 (PDE5) inhibitors, e.g., sildenafil
13. If a CT/MR scan has already been performed, then it shows a non-stroke lesion that explains the acute presentation.
14. Known previous enrolment in ENOS-2

## **21 Recruitment**

Recruitment will be summarised in a CONSORT flow diagram.

## **22 Withdrawal/follow-up**

Withdrawals, and missed follow-ups and their timing will be summarised in the CONSORT flow diagram.

## **23 Baseline patient characteristics**

These will comprise demographics and clinical measures (**see Table 1**).

Summarisation of data will be shown as number (%), median [interquartile range] or mean (standard deviation), as appropriate.

## **SECTION 6. ANALYSIS**

### **24 Outcome definitions**

#### ***24a Primary endpoint***

The primary end point of the study is the feasibility of recruiting and treating 120 patients (100 IS, 20 ICH) between 3 and 5 hours after stroke.

#### ***24b Secondary endpoints***

1. Hospital admission:
  - Neurological impairment (NIHSS)
  - Systolic and diastolic blood pressure, heart rate.
  - Proportion of participants with systolic blood pressure <185 mmHg.
  - Feeding and dysphagia (dysphagia severity rating scale)
  - Stroke lesion size on brain scan (non-contrast CT or T2 MR).
  - Amount of cerebral arterial patency on brain scan (CT or MR angiography).
2. Hospital utilisation:
  - Open-label blood pressure lowering.
  - Intravenous thrombolysis.
  - Mechanical thrombectomy.
  - Hyperacute stroke unit.
  - Stroke Rehabilitation Unit.
  - Physiotherapy.
  - Occupational therapy.
  - Speech & language therapy.
  - Surgery for IS - Hemicraniectomy.
  - Surgery for ICH.
  - Days in intensive/critical care unit.
3. At day 2:
  - Systolic and diastolic blood pressure, heart rate.

4. At day 2: Biomarkers
  - Blood biomarkers (exact measures to be determined by literature review prior to measurement but examples include S-100, NOx).
  - Genetic markers (exact measures to be determined by literature review prior to measurement but examples include NO synthase polymorphisms).
5. At day 2 (or discharge if sooner):
  - Neurological impairment (NIHSS).
  - Stroke recurrence.
  - Neurological deterioration from baseline (NIHSS  $\geq 4$  points, or  $\geq 2$ -point increase in any domain).
  - Feeding and dysphagia (DSRS).
6. At discharge/death
  - Length of stay in hospital.
  - Patient disposition.
7. At day 90 by telephone (or post):
  - Dependency – modified Rankin Scale (primary clinical endpoint at Day 90).
  - Disability/activities of daily living - Barthel Index (BI).
  - Quality of life - health utility status (HUS, derived from EuroQoL-5D), EQ-Visual Analogue Scale (EQ-VAS).
  - Cognition - telephone-MMSE, telephone interview cognition scale (TICS), animal naming.
  - Mood - Zung depression scale.
  - Patient disposition (died, institution/in hospital, home).

### **24c Safety endpoints**

1. By day 2
  - Any serious adverse event.
  - Headache.
  - Infection (pneumonia/chest, urinary tract, other).
  - Hypotension requiring clinical intervention.
  - Hypertension requiring clinical intervention.
2. From day 3 to day 90
  - Any fatal serious adverse event.

Data on stroke recurrence and acute coronary syndrome, termed safety outcome events, will be collected up to day 90.

**24d Units:** Units will be shown in tables.

**24e Calculations/transformations:** Quality of life using UK weightings.

## **25 Analysis methods**

### **25a Method analyses of outcomes**

ENOS-2 is a feasibility trial, and the main analyses will present descriptive statistics and comparisons between treatment groups. Counts will be summarised using frequencies N and percentages %, ordinal variables will be summarised using median [interquartile range] and continuous variables using means (standard deviation). Central tendency, comparisons and regressions will be summarised and analysed as follows (**Table D**).

**Table D. Descriptive and analytical statistics**

	Nominal	Binary	Ordinal	Continuous	Time to Event
Central tendency	N (%)	N (%)	Median [interquartile	Mean (standard	N (%)

and distribution			range]	deviation)	
Comparisons	Chi-square (2x2, or rxc)	Chi-square (2x2)	Mann-Whitney U	t-test (pooled) change from baseline-Repeat Measures (RM)	
Regression	-	Binary logistic regression (BLR)	Ordinal logistic regression (OLR)	Multiple linear regression (MLR)	Cox proportional hazards regression (CPHR)

### **25b Analyses of Primary endpoint**

Recruitment, treatment and follow-up rates will be estimated using tabulation and graphical presentation.

It is likely that a large definitive trial would be feasible if at least 70 participants were recruited into this study, that compliance with randomised treatment was high and that a high proportion of follow-up data was available.

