## SYNOPSIS

Title	Efficacy of Nitric Oxide in Stroke-2 (ENOS-2)
Acronym	ENOS-2
Short title	Efficacy of Nitric Oxide in Stroke-2 (ENOS-2)
Chief Investigator	[name] Deputy Chief Investigator: [name]
Objectives	To assess the feasibility of recruitment and safety of transdermal glyceryl trinitrate (GTN) versus sham applied between 3 and 5 hours of stroke to inform a definitive trial.
Trial Configuration	Prospective randomised single-blinded masked-endpoint phase IIb trial.
Setting	Adults with hyperacute stroke presenting at emergency departments and hyperacute stroke units in England.
Sample size estimate	This is a feasibility study so there is no formal sample size calculation. (But recruitment of 100 participants would allow an adjusted common odds ratio, acOR 0.51 to be detected, assuming mRS distribution as in  ; alpha 0.05, power 0.80.)  It is likely that a large definitive trial would be feasible if at least 70 participants were recruited into this study. Lower recruitment would not preclude progression if there was some evidence that the barriers to recruitment identified could be overcome.
Number of participants	
 
• 100 with ischaemic stroke (50 randomised to GTN, 50 randomised to sham)
 
• 20 with intracerebral haemorrhage (for safety) (10 randomised to GTN, 10 randomised to sham)
 

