## **DURATION OF THE TRIAL / STUDY AND PARTICIPANT INVOLVEMENT**

**Participant Duration:** The study will recruit patients for 31 months. The participant's involvement in the trial will last for 3 months, from randomisation (day 1) until final follow-up at 90 days. Treatment will last 2 days (enrolment day and next day).

**Study Duration:** The study will recruit patients for 31 months. The participant's involvement in the trial will last for 3 months, from randomisation (day 1) until final follow-up at 90 days.

Treatment will last 2 days (enrolment day and next day). Total study duration will be 36 months.

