## **STATISTICS**

### **Methods**

Data will be analysed by a qualified statistician who is blinded to treatment allocation, using a validated software package. A statistical analysis plan (SAP) will be agreed prior to database lock and release of randomisation codes. The trial will be reported in accordance with CONSORT guidelines including the extension to pilot and feasibility trials, as appropriate.

This is a feasibility trial, and the main analysis will be with descriptive statistics; comparisons between treatment groups will also be performed. Results will be summarised and analysed as follows:

- Counts will be summarised using frequency and percentage (N, %) and compared with binary logistic regression.
- Time to event analyses will be summarised using frequency and percentage (N, %) and compared with Cox proportional hazards regression.
- Ordered categorical variables will be summarised using median [interquartile range] and compared with ordinal logistic regression.
- Continuous variables will be summarised using mean (standard deviation) and compared with multiple linear regression.

We will assess the feasibility of recruiting, treating, and following up patients from 2 centres over three years. We will estimate a recruitment rate, treatment rate and follow-up rate. It is likely that a large definitive trial would be feasible if at least 75 participants were recruited into this study, that compliance with randomised treatment was high and that a high proportion of follow up data was available. Lower recruitment would not preclude progression if there was evidence that the barriers to recruitment identified could be overcome.

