### **Sample size and justification**

Since this is a feasibility study with one of the objectives being to determine potential recruitment rates, a formal sample size calculation is not appropriate. If more than 75 participants are randomised from 2 centres over a 31-month period, it is likely that a larger study recruiting approximately 500 participants in around 20 centres would be feasible. Depending on the final sample size calculation for the definitive study, the number of centres and recruitment period could be determined using the information from the rates and patterns observed in the feasibility study.

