**Table 2. Feasibility measures.**

Data are number (%).

Recruitment of 100 IS patients, 20. We will assess the feasibility of recruiting, treating, and following up patients from 2 centres over three years. We will estimate a recruitment rate, treatment rate and follow-up rate. It is likely that a large definitive trial would be feasible if at least 70 participants were recruited into this study, that compliance with randomised treatment was high and that a high proportion of follow up data was available.

Measure	Metric	N	Achieved
Recruitment			
Overall			xxx/120 (xxx)
Target patients	100 with IS patients		xxx/100 (xxx)
	20 with ICH		xxx/20(xxx)
Primary			
Retention of enrollees at Day 90 (follow-up)	>70 participants	xxx	xxx /100 (xxx)
Treatment compliance/ adherence			
Received GTN	All 2 days treatment	xxx	xxx (xxx)
	First day treatment	xxx	xxx (xxx)
Co-enrolment			
MAPS-2	n(%)		xxx (xxx)
PhEAST	n(%)		xxx (xxx)
ReCAST-3	n(%)		xxx (xxx)
TICH-3	n(%)		xxx (xxx)
MACE-ICH	n(%)		xxx (xxx)
TRIDENT	n(%)		xxx (xxx)
ABC-ICH	n(%)		xxx (xxx)
ENRICH-AF	n(%)		xxx (xxx)
ATTEST-I	n(%)		xxx (xxx)
TASTE	n(%)		xxx (xxx)
OPTIMAS	n(%)		xxx (xxx)
ProFATE	n(%)		xxx (xxx)
Mrna-1273-P305	n(%)		xxx (xxx)
COMMITTS	n(%)		xxx (xxx)
OPTIMIST	n(%)		xxx (xxx)

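### The recruitment threshold for a definitive trial takes three values (at least 70, at least 75, more than 75), and SAP Table 2 prints the 70 against Day-90 retention

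*SAP*

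**What the plan says.** Five places state how many participants would make a definitive trial likely to be feasible.

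- Protocol Synopsis, sample size estimate: "would be feasible if at least 70 participants were recruited into this study".
- SAP 25b, and again the text above SAP Table 2: "It is likely that a large definitive trial would be feasible if at least 70 participants were recruited into this study".
- Protocol Statistics, Methods: "It is likely that a large definitive trial would be feasible if at least 75 participants were recruited into this study".
- Protocol, Sample size and justification: "If more than 75 participants are randomised from 2 centres over a 31-month period", a study of about 500 participants in about 20 centres is likely to be feasible.

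The Synopsis and protocol Methods add that a lower count need not prevent progression if the obstacles to recruitment look surmountable. The SAP does not repeat this. Protocol Methods, SAP 25b and the Table 2 text also ask for high compliance and a high proportion of follow-up data.

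The body of SAP Table 2 is laid out differently from its own introductory text. The recruitment rows show achievement against 120, 100 and 20. Under the label Primary, the row "Retention of enrollees at Day 90 (follow-up") carries the metric of more than 70 participants, with the result shown out of 100.

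**The concern.** The progression criterion for the primary endpoint should be one figure, fixed before the count is known. Here it is three. The sentences in protocol Methods and SAP 25b are nearly identical apart from the number, so they cannot be read as two criteria for two purposes. Neither document says which figure governs. If accrual ends in the affected range, whoever writes the report has to choose the threshold after seeing the count.

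The allowance for lower recruitment makes a single figure more useful. Without one, a reader cannot tell whether the criterion was met or the exception was used.

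Table 2 adds a second problem. A count of people retained, set against a fixed 100, measures neither recruitment nor retention.

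**Working it through.** The thresholds are asserted without a formula, and no recruitment duration is given for the definitive trial. There is no derivation to reproduce, so the check compares the rules count by count.

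**Recruitment rules**

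| Final count | At least 70 (Synopsis, SAP 25b, Table 2 text) | At least 75 (protocol Methods) | More than 75 (protocol sample size) |
|---|---|---|---|
| 69 or fewer | not met | not met | not met |
| 70 to 74 | met | not met | not met |
| 75 | met | met | not met |
| 76 or more | met | met | met |

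The rules disagree at six counts, 70 to 75 inclusive.

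**How likely is a count in that range?** The documents give no expected accrual apart from the target of 120, so the mean is an assumption. With a Poisson count X of mean m, P(70 ≤ X ≤ 75) = F(75; m) − F(69; m), where F is the cumulative distribution function.

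| Assumed mean m | P(70 to 75) |
|---|---|
| 65 | 18.5% |
| 70 | 26.4% |
| 72 | 27.5% |
| 75 | 26.4% |
| 80 | 19.4% |
| 90 | 4.7% |
| 100 | 0.5% |
| 120 (the target) | under 0.001% |

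**Table 2 retention row, read literally.** More than 70 retained means at least 71. With n recruited, the retention needed is 71/n.

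- n = 70: 71/70 is above 1, so the row cannot be met even if all 70 are followed.
- n = 75: 71/75 = 94.7%.
- n = 76: 71/76 = 93.4%.
- n = 100: 71/100 = 71.0%.
- n = 120: 71/120 = 59.2%.

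The retention demanded therefore falls as recruitment rises. A trial with 76 recruited meets all three recruitment rules and can still fail this row, while a full trial that lost about four in ten participants (49/120 = 40.8%) would pass it. The printed denominator of 100 matches the ischaemic target, but neither the 120 to be enrolled nor the number actually randomised.

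**Periods.** The protocol's section on duration says "The study will recruit patients for 31 months" within a total of 36 months. The phrase "following up patients from 2 centres over three years" belongs to a sentence that covers recruiting, treating and following up, which is the whole study. The two statements fit together.

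**The case against.** The strongest reply is that this is not a stopping rule. Each sentence says only that feasibility is likely, and the protocol leaves progression open below the threshold. That stands: a reader might infer that 70 to 74 recruits would end the programme, and the documents do not support this. The softness does not tell anyone which figure applies, however, and the SAP leaves out the sentence that creates it.

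The second reply is that the row in Table 2 is a labelling slip in a shell, because the text above it and SAP 25b both attach 70 to recruitment. The intention can probably be recovered. But this row is the only place where follow-up is given a number, so a literal reading would be an easy mistake.

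Some stronger readings should be set aside.

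- The conflict is not simply protocol against SAP. The protocol itself holds 70, at least 75 and more than 75, so giving the SAP precedence would leave the protocol inconsistent.
- The 31 months and the three years do not contradict each other.
- This is not the plan's only feasibility figure. There is also the target of 120, and SAP 16a sets adherence at 90% or more receiving the first treatment.
- The sample-size section links its figure to the 500-participant trial, but nothing there shows that 75 supports such a trial and 70 does not.

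**Conclusion.** Wrong as written. Three different recruitment thresholds apply to one judgement on the primary endpoint, and they disagree at counts of 70 to 75. The disagreement matters only if accrual ends near the threshold. The figure of about 26% rests on a Poisson count and an assumed mean of 70 to 75, close to the worst case; it should not be read as a forecast, and at the planned 120 the chance is negligible. The Table 2 fault does not depend on any accrual assumption: the row as printed rejects complete follow-up of 70 and accepts 59.2% follow-up of 120. Neither fault biases a treatment comparison, and the recruitment, treatment and follow-up rates can be estimated whichever figure is chosen. What is lost is a prespecified basis for saying that the feasibility criterion was met.

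**What to change.** Make these changes before the final count is known.

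1. Choose one threshold with one inequality, give the reason for it, and use it in the Synopsis, protocol Methods, protocol Sample size and justification, SAP 25b and the text above SAP Table 2. The documents do not determine which figure is right; consistency and a stated justification are what is needed.
2. Carry the protocol's sentence allowing progression at lower recruitment into SAP 25b, so that meeting the criterion and using the exception can be reported as different things.
3. In SAP Table 2, move the threshold to the overall recruitment row.
4. In the same table, report retention as participants with a Day-90 mRS divided by participants randomised, with a 95% confidence interval, against a percentage criterion stated in advance.
5. State that the recruitment rate is computed over the recruitment period, in centre-months open. This is a clarification only.

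The cost is wording in two documents and the relabelling of two rows in one table shell. If 75 is chosen, the hurdle rises by 5 participants where the text now says 70. No new data are needed.

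### The recruitment benchmark for a likely feasible definitive trial is at least 70, at least 75 or more than 75 depending on the section, so final counts of 70 to 75 meet some versions and miss others

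*SAP*

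**What the plan says.** Recruitment feasibility is the primary objective (Protocol, Primary objective) and the primary endpoint (Protocol, Primary endpoint; SAP 24a), with a target of 120 patients: 100 ischaemic stroke (IS) and 20 intracerebral haemorrhage (ICH). The count at which a definitive trial is judged likely to be feasible appears in five places:

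- Protocol synopsis, sample size row: "It is likely that a large definitive trial would be feasible if at least 70 participants were recruited into this study".
- Protocol, Statistics, Methods: "feasible if at least 75 participants were recruited into this study, that compliance with randomised treatment was high", with a further condition on follow-up data. The same paragraph speaks of 2 centres over three years.
- Protocol, Sample size and justification: "If more than 75 participants are randomised from 2 centres over a 31-month period", a study of about 500 participants in around 20 centres is likely to be feasible.
- SAP 25b: "a large definitive trial would be feasible if at least 70 participants were recruited into this study", with the compliance and follow-up conditions. It names no centres and no period.
- SAP Table 2, introductory text: "feasible if at least 70 participants were recruited into this study, that compliance with randomised treatment was high", again with 2 centres over three years.

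In the Table 2 shell, the recruitment rows show only results out of 120, 100 and 20. The metric of more than 70 participants stands under the label Primary, on the row "Retention of enrollees at Day 90 (follow-up"), with a result cell out of 100.

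The synopsis and Protocol Methods add that lower recruitment would not rule out progression if the barriers could be overcome. SAP 25b and Table 2 omit this.

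**The concern.** The count is the only numerical benchmark in the rule for the trial's primary question. The companion conditions, high compliance and a high proportion of follow-up data, carry no number there. (SAP 16a defines sufficient adherence as at least 90% receiving the first treatment, but does not link it to this rule.)

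The values differ within the protocol as well as between protocol and SAP, so giving one document precedence does not settle the matter. At stake is how the primary result is reported. With 72 recruited, for example, one report could say that the benchmark was met, citing the SAP, and another that it was missed, citing the protocol body. Both would be faithful to current text, and the choice could be made after the count is known. A reader of Table 2 could also take the benchmark to concern retention.

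**Working it through.** **No figure to reproduce.** Neither document derives 70 or 75. Protocol Sample size says that a formal calculation is not appropriate.

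**Step 1. Apply each recruitment version to each possible final count.** More than 75 means at least 76.

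| Final count | At least 70 (synopsis, SAP 25b, Table 2 text) | At least 75 (Methods) | More than 75 (Sample size) |
|---|---|---|---|
| 69 or fewer | missed | missed | missed |
| 70 to 74 | met | missed | missed |
| 75 | met | met | missed |
| 76 or more | met | met | met |

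Six counts, 70 to 75, get conflicting answers.

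**Step 2. How often the wording would matter.** The documents give no expected count, so I assume a Poisson count N with mean m and show a range. The gap is P(N ≥ 70) − P(N ≥ 76).

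| Assumed mean m | P(N ≥ 70) | P(N ≥ 76) | Gap (percentage points) |
|---|---|---|---|
| 50 | 0.004 | 0.000 | 0.4 |
| 60 | 0.112 | 0.026 | 8.6 |
| 72 | 0.609 | 0.334 | 27.5 |
| 73 | 0.653 | 0.378 | 27.5 |
| 80 | 0.881 | 0.688 | 19.4 |
| 90 | 0.987 | 0.940 | 4.7 |
| 100 | 0.999 | 0.995 | 0.5 |
| 120 (target) | 1.000 | 1.000 | 0.0 |

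The gap peaks near m = 72.5.

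**Step 3. Does the definitive trial favour one number?** Rate per centre-month = n / (2 × months). Months to recruit 500 in 20 centres = 500 / (20 × rate).

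| n | Period (months) | Rate per centre-month | Months to 500 |
|---|---|---|---|
| 70 | 31 | 70/62 = 1.13 | 22.1 |
| 75 | 31 | 75/62 = 1.21 | 20.7 |
| 76 | 31 | 76/62 = 1.23 | 20.4 |
| 70 | 36 | 70/72 = 0.97 | 25.7 |
| 75 | 36 | 75/72 = 1.04 | 24.0 |
| 76 | 36 | 76/72 = 1.06 | 23.7 |

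For a fixed period, moving from 70 to 76 changes the projection by 1.7 months over 31 months (22.1 − 20.4) and 2.0 months over 36 (25.7 − 23.7). For a fixed count of 70, moving from 31 to 36 months changes it by 3.6 months (25.7 − 22.1). The period therefore matters more than the count, and the projection does not choose between 70 and 75.

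**Step 4. Read the Table 2 retention row literally.** More than 70 retained means at least 71.

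- 70 recruited: 71/70 = 101.4%, impossible even with complete follow-up.
- 75 recruited: 71/75 = 94.7% retention needed.
- 120 recruited: 71/120 = 59.2% retention needed.

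A fixed count demands less retention the more patients are recruited, so it does not measure retention. Exactly 70 recruits would meet the text above the table and could never meet the row.

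**The case against.** The strongest case on the other side is that this is a soft planning statement. Every version says likely, and none says that a lower count makes the trial infeasible. The synopsis and Protocol Methods expressly allow progression below the count. Protocol Sample size is a one-way statement, so missing it yields no negative verdict. SAP 25b will also report recruitment, treatment and follow-up rates, and Protocol Sample size says these can set the number of centres and the period of the definitive trial. Planning does not rest on the count alone. This stands: a reader might infer that the same result would be declared feasible under one document and not feasible under the other, and the documents do not support that. What remains is that a benchmark on the primary endpoint needs one value even if it is soft. The documents also differ on how soft it is, because the SAP drops the clause on lower recruitment.

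A reader might infer that 75 is the true value because Protocol Sample size ties it to a centre number and a definitive design. Only the definitive design is unique to that section; Protocol Methods and Table 2 also name 2 centres. That section says more than 75, not at least 75, and Step 3 does not separate the numbers. Three of the five statements say 70.

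On Table 2, no text makes the retention row a decision rule, and the paragraph above it gives 70 as a recruitment count. Step 4 shows what the row would mean if read literally, not what the trial will decide. The conflict in Step 1 does not depend on it.

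Three years may mean total duration, since the protocol elsewhere gives 31 months of recruitment within 36. That is plausible, but the text beside the count does not say so.

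**Conclusion.** Wrong as written. Current text holds three versions of the recruitment benchmark and two periods beside it, and Table 2 attaches the number to the wrong row. The effect is confined to final counts of 70 to 75. Under the Poisson assumption, the wording alone moves the chance of meeting the benchmark by at most about 27 percentage points. That is the worst case, at a mean of 72 to 73; the gap is negligible at a mean of 50 or above 100. The result is a criterion met or not met, not a formal go/no-go. No treatment-effect estimate, analysis population or participant safety is affected. The six conflicting counts follow from the text alone; only the probabilities rest on the assumed distribution and mean.

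**What to change.** Before database lock:

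1. The sponsor chooses one threshold, 70 or 75, with one inequality, and says whether it counts IS and ICH patients together. The documents do not settle the value.
2. The sponsor chooses one recruitment period, reconciling 31 months with three years.
3. Both are stated identically in the protocol synopsis, Protocol Methods, Protocol Sample size, SAP 25b and SAP Table 2.
4. The figure of 120 (100 + 20) is labelled as the target and the chosen number as the benchmark.
5. In Table 2, the threshold moves to the recruitment row, and Day-90 retention is expressed as a proportion of those randomised.
6. The clause allowing progression with lower recruitment is either carried into the SAP or removed from the protocol.

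The cost is wording only: an SAP revision and a protocol amendment, with no new data and no change to participant care.
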